10.7 Appendix 7: Country-specific Requirements

10.7.1 Saudi Arabia and United Arab Emirates Requirements

The protocol change outlined in this section is being made to align with legal and cultural mores in Saudi Arabia and United Arab Emirates:

Pregnancy Testing

All married female participants (or female participants who in the clinical opinion of the investigator could be pregnant) will have a urine pregnancy test at the visits indicated in the SoA.

10.7.2 Serum Pregnancy Requirements

Pregnancy Testing

If required by the Health Authorities and/or IRBs/ECs, female participants from those countries/sites (eg, United Kingdom, Guatemala) will have a serum pregnancy test performed to determine eligibility instead of a urine pregnancy test.

10.8 Appendix 8: BMI for Age Charts

Sites should follow their approved country-specific BMI-for-age percentile charts, if available (eg, sites within the US will refer to the Centers for Disease Control charts). If an approved country-specific BMI-for-age percentile chart is not available, refer to the WHO charts shown in Figure 2 and Figure 3.

Instructions for obtaining the body mass index-for-age percentile:

- Find the child's age on the horizontal axis
- Find the BMI measurement on the vertical axis (to determine BMI, refer to Section 8.2.4).
- The body mass index-for-age percentile will be at the intersection of the child's age and BMI measurement.

Figure 2 BMI for Age Girls, 5 to 19 Years (Percentiles)

[figure not shown]
World Health
Organization

Ref: [deOnis, M. 2007]

Figure 3 BMI for Age Boys, 5 to 19 Years (Percentiles)

Ref: [deOnis, M. 2007]

10.9 Appendix 9: Blood Pressure Tables

Table 11 Blood Pressure Table for Gender/Age/Height for Boys Age 10 to 17

Years of Age	Blood Pressure	Systolic Blood Pressure by Percentile of Height (mmHg)							Diastolic Blood Pressure by Percentile of Height (mmHg)							
(Years)	Percentile	5%	10%	25%	50%	75%	90%	95%	5%	10%	25%	50%	75%	90%	95%	
10	90th	111	112	114	115	117	119	119	73	73	74	75	76	77	78	
	95th	115	116	117	119	121	122	123	77	78	79	80	81	81	82	
	99th	122	123	125	127	128	130	130	85	86	86	88	88	89	90	
11	90th	113	114	115	117	119	120	121	74	74	75	76	77	78	78	
	95th	117	118	119	121	123	124	125	78	78	79	80	81	82	82	
	99th	124	125	127	129	130	132	132	86	86	87	88	89	90	90	
12	90th	115	116	118	120	121	123	123	74	75	75	76	77	78	79	
	95th	119	120	122	123	125	127	127	78	79	80	81	82	82	83	
	99th	126	127	129	131	133	134	135	86	87	88	89	90	90	91	
13	90th	117	118	120	122	124	125	126	75	75	76	77	78	79	79	
	95th	121	122	124	126	128	129	130	79	79	80	81	82	83	83	
	99th	128	130	131	133	135	136	137	87	87	88	89	90	91	91	
14	90th	120	121	123	125	126	128	128	75	76	77	78	79	79	80	
	95th	124	125	127	128	130	132	132	80	80	81	82	83	84	84	
	99th	131	132	134	136	138	139	140	87	88	89	90	91	92	92	
15	90th	122	124	125	127	129	130	131	76	77	78	79	80	80	81	
	95th	126	127	129	131	133	134	135	81	81	82	83	84	85	85	
	99th	134	135	136	138	140	142	142	88	89	90	91	92	93	93	
16	90th	125	126	128	130	131	133	134	78	78	79	80	81	82	82	
	95th	129	130	132	134	135	137	137	82	83	83	84	85	86	87	
	99th	136	137	139	141	143	144	145	90	90	91	92	93	94	94	
17	90th	127	128	130	132	134	135	136	80	80	81	82	83	84	84	
	95th	131	132	134	136	138	139	140	84	85	86	87	87	88	89	
	99th	139	140	141	143	145	146	147	92	93	93	94	95	96	97	
Note: co	Note: country-specific Blood Pressure norms may be used; otherwise, these guidelines should be used.															

Ref: [National High Blood Pressure Education Program Working Group on 2004]

Table 12 Blood Pressure Table for Gender/Age/Height for Girls Age 10 to 17

Years of Age	Blood Pressure	Systolic Blood Pressure by Percentile of Height (mmHg)								Diastolic Blood Pressure by Percentile of Height (mmHg)							
(Years)	Percentile	, ,							5%	10%	25%	50%	75%	90%	95%		
10	90th	112	112	114	115	116	118	118	73	73	73	74	75	76	76		
	95th	116	116	117	119	120	121	122	77	77	77	78	79	80	80		
	99th	123	123	125	126	127	129	129	84	84	85	86	86	87	88		
11	90th	114	114	116	117	118	119	120	74	74	74	75	76	77	77		
	95th	118	118	119	121	122	123	124	78	78	78	79	80	81	81		
	99th	125	125	126	128	129	130	131	85	85	86	87	87	88	89		
12	90th	116	116	117	119	120	121	122	75	75	75	76	77	78	78		
	95th	119	120	121	123	124	125	126	79	79	79	80	81	82	82		
	99th	127	127	128	130	131	132	133	86	86	87	88	88	89	90		
13	90th	117	118	119	121	122	123	124	76	76	76	77	78	79	79		
	95th	121	122	123	124	126	127	128	80	80	80	81	82	83	83		
	99th	128	129	130	132	133	134	135	87	87	88	89	89	90	91		
14	90th	119	120	121	122	124	125	125	77	77	77	78	79	80	80		
	95th	123	123	125	126	127	129	129	81	81	81	82	83	84	84		
	99th	130	131	132	133	135	136	136	88	88	89	90	90	91	92		
+15	90th	120	121	122	123	125	126	127	78	78	78	79	80	81	81		
	95th	124	125	126	127	129	130	131	82	82	82	83	84	85	85		
	99th	131	132	133	134	136	137	138	89	89	90	91	91	92	93		
16	90th	121	122	123	124	126	127	128	78	78	79	80	81	81	82		
	95th	125	126	127	128	130	131	132	82	82	83	84	85	85	86		
	99th	132	133	134	135	137	138	139	90	90	90	91	92	93	93		
17	90th	122	122	123	125	126	127	128	78	79	79	80	81	81	82		
	95th	125	126	127	129	130	131	132	82	83	83	84	85	85	86		
	99th	133	133	134	136	137	138	139	90	90	91	91	92	93	93		
Note: cou	Note: country-specific Blood Pressure norms may be used; otherwise, these guidelines should be used.																

Ref: [National High Blood Pressure Education Program Working Group on 2004]

143

10.10 Appendix 10: Management of Participants with Elevated Liver Enzymes (ALT or AST ≥3x ULN)

Section I: Identification and Management of Participants with ALT or AST Results $\geq 3X$ ULN

Increases in ALT or AST $\ge 3X$ the ULN are defined as clinically significant for this study. The central laboratory report will alert the investigator if a participant meets this threshold. When a randomized participant who is receiving blinded investigational product has an ALT or AST elevation beyond the clinical significant margin above, the investigator should monitor the participant according to the instructions below and discontinue the participant from blinded investigational product if a prespecified criterion is met.

The investigator should select the appropriate set of instructions (either A, B, or C below) for managing a participant with elevated liver enzymes based upon the following factors: (1) the magnitude of a participant's ALT or AST elevation, (2) the presence or absence of symptoms, (3) whether there is a corresponding increase in total bilirubin $\geq 2X$ ULN.

Investigator Instructions for Management of Participants with ALT or AST $\geq 3X$ ULN

A) Participant has:

- ALT or AST \geq 3X ULN with total bilirubin \geq 2X ULN and ALP \leq 2X ULN
 - 1. The participant should *interrupt* blinded investigational product.
 - 2. Refer to the "Event of Clinical Interest (ECI) Guidance for Potential DILI (Drug-Induced Liver Injury) in Clinical Trials" (located in the Investigator Trial File Binder or equivalent) and perform procedures accordingly.
 - 3. If an etiology for the elevated ALT or AST and total bilirubin levels is established and the abnormalities resolve, blinded investigational product may be restarted with approval by the Sponsor. Otherwise, the participant should discontinue treatment with blinded investigational product.

Note: Laboratory assessments prescribed in the *Event of Clinical Interest (ECI) Guidance* for *Potential DILI (Drug-Induced Liver Injury) in Clinical Trials* may be sent locally in emergent cases and to support participant compliance with the necessary evaluations. Participants unwilling or unable to undergo the prescribed testing should be discontinued from treatment with blinded investigational product.

B) Participant has:

- ALT or AST ≥8X ULN OR
- ALT or AST ≥3X ULN and signs or symptoms of a drug reaction consistent with liver injury (eg, fever, eosinophilia, right upper quadrant pain, dark urine, fatigue, etc.)
 - 1. The participant should *interrupt* blinded investigational product.
 - 2. Perform repeat ALT and AST within 3 days of receipt of the laboratory report.
 - 3. Initiate evaluation for potential causes. See Section II below.
 - 4. Repeat ALT and AST tests at appropriate intervals, initially approximately 2-times per week, until resolution or return to baseline.
 - 5. If an etiology for the elevated liver enzymes is established (eg, active hepatitis with specific etiology demonstrated, cholecystitis, biliary obstruction), blinded investigational product may be restarted with approval by the Sponsor. Otherwise, the participant should discontinue treatment with blinded investigational product.

Note: Local laboratory assessments can be used to support compliance with the repeat testing procedure described above if required. Participants unwilling or unable to undergo repeat ALT and AST testing at the frequency recommended above should be discontinued from treatment with blinded investigational product.

C) Participant has:

- ALT or AST ≥3X and <8X ULN
- 1. For participants with:

ALT or AST \geq 3X *and* \leq 5X *ULN:*

• Perform repeat ALT and AST within 3-5 days of receipt of the laboratory report.

OR

ALT or AST \geq 5*X ULN and* \leq 8*X ULN*:

- Perform repeat ALT and AST within 3 days of receipt of the laboratory report. Participants unable to undergo repeat measurements within 3 days *must interrupt* blinded investigational product.
- 2. Initiate evaluation for potential causes. See Section II below.
- 3. Actions based upon *initial* repeat testing:
 - If ALT or AST ≥3X ULN with total bilirubin ≥2X ULN, then interrupt blinded investigational product and monitor as described in the Section A Instructions above and also per the "Event of Clinical Interest (ECI) Guidance for Potential DILI (Drug-Induced Liver Injury) in Clinical Trials" (located in the Investigator Trial File Binder or equivalent) and perform procedures accordingly.

146

PRODUCT: MK-8835
PROTOCOL/AMENDMENT NO.: 059-04

- If ALT or AST ≥8X ULN or ALT or AST ≥3X ULN with symptoms present (eg, fever, eosinophilia, right upper quadrant pain, dark urine, fatigue, etc.), then interrupt blinded investigational product and monitor as described in the Section B Instructions above.
- If ALT or AST ≥3X ULN and <8X ULN (without above criteria met), continue to measure ALT and AST 1- to 2-times per week (2-times per week if ALT or AST ≥5X ULN or if an increase >20% occurred since the first elevated value[s]).
- If ALT and AST > ULN and <3X ULN, perform repeat determination in 5-7 days, and then at appropriate intervals (eg, every other week) until the participant's ALT and AST levels are within normal limits or are similar to baseline.
- 4. Actions based upon *follow-up* repeat testing:
 - If **ALT or AST ≥5X ULN** after 2 weeks, discontinue blinded investigational product.
 - If **ALT or AST remain elevated** (≥3X and <5X ULN) but stable, the frequency of retesting can decrease (eg, every other week) with approval from the Sponsor.
 - If ALT and AST >ULN and <3X ULN, perform repeat determination in 5-7 days, and then at appropriate intervals (eg, every other week) until the participant's ALT and AST levels are within normal limits or are similar to baseline.

Note: Local laboratory assessments can be used to support compliance with the repeat testing procedures described above if required. Participants unwilling or unable to undergo repeat ALT and AST testing at the frequency defined above should be discontinued from treatment with blinded investigational product.

In summary, participants should be discontinued from blinded investigational product for any of the following reasons:

- ALT or AST \ge 3X ULN with total bilirubin \ge 2X ULN and ALP <2X ULN and without an established etiology
- ALT or AST \geq 8X ULN or \geq 3X ULN with symptoms consistent with liver injury and without an established etiology
- ALT or AST \geq 5X ULN for 2 weeks or longer

Section II: Guidance for Assessment of Potential Etiology

Questions to Assess Etiology

Investigate potential causes for the participant's elevated liver enzymes using the questions below. Answers to the questions should be recorded in the participant's source documents and appropriate eCRFs.

- 1. Has the participant recently:
 - Had a change in his/her pattern of alcohol use? Investigate historic pattern of alcohol use as well.
 - Administered an illegal drug(s) (including intravenous drugs)?
 - Been exposed to a chemical agent or other environmental toxin?
 - Consumed any unusual foods (eg, mushrooms), seasonal foods, or initiated treatment with new herbal/nutritional supplements?
 - Initiated a new diet regimen, started a rigorous exercise program, or experienced any form of severe physical exertion?
 - Traveled to another country or region?
- 2. Does the participant have a relevant concomitant illness (eg, cholelithiasis, hepatitis, etc.) or has the participant had potential exposure to viral hepatitis (transfusion, tattoo, new sexual partner)?
- 3. Does the participant have a relevant medical history (eg, autoimmune disorder, cancer, Gilbert's syndrome, obesity, Wilson's disease, NASH, alcoholic or infectious hepatitis, biliary tract disease, hypoxic/ischemic hepatopathy, etc.)?
- 4. Has the participant recently been treated with a concomitant medication(s) with demonstrated or suspected effects on the liver (eg, acetaminophen; amiodarone; aspirin; chlorpromazine; dantrolene; erythromycin; halothane; isoniazid; methyldopa; nitrofurantoin; oxyphenisatin; perhexiline maleate; phenytoin; propylthiouracil; rifampin; sulfonamides; tetracyclines) or initiated treatment with another new medication(s)?

Additional Laboratory/Imaging Evaluations

In participants for whom an etiology for the abnormal liver enzymes is unknown or whose elevated liver enzymes persist for more than 1-week:

- 1. Consider performing serologic tests including: (a) Hepatitis A (IgM); (b) Hepatitis B (surface antigen and core IgM); (c) Hepatitis C (antibody); (d) Hepatitis E (IgG and IgM). Obtain consent prior to testing, if required locally. Additional evaluations may be performed at the discretion of the investigator.
- 2. Consider an ultrasound of the participant's right upper quadrant and additional scans (endoscopic retrograde cholangiopancreatography [ERCP] or magnetic resonance cholangiopancreatography [MRCP]) if needed.

Note: Participants may also be referred to a gastroenterologist or hepatologist for an additional work-up if considered necessary by the investigator.

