7 DISCONTINUATION OF STUDY INTERVENTION AND PARTICIPANT WITHDRAWAL

7.1 Discontinuation of Study Intervention

Discontinuation of study intervention does not represent withdrawal from the study.

As certain data on clinical events beyond study intervention discontinuation may be important to the study, they must be collected through the participant's last scheduled follow-up, even if the participant has discontinued study intervention. Therefore, all participants who discontinue study intervention prior to completion of the protocol-specified treatment period will still continue to participate in the study as specified in Section 1.3.

Participants may discontinue study intervention at any time for any reason or be discontinued from the study intervention at the discretion of the investigator should any untoward effect occur. In addition, a participant may be discontinued from study intervention by the investigator or the Sponsor if study intervention is inappropriate, the study plan is violated, or for administrative and/or other safety reasons. Specific details regarding procedures to be performed at study intervention discontinuation are provided in Section 8.1.9 and Section 8.10.8. Participants who discontinue study medication without withdrawing consent will have their diabetes managed as considered clinically appropriate by their primary doctor. Initiation of other AHAs will not be considered as prohibited medication in these participants. Participants who discontinue study medication before **Visit 5/Week 12** will not have the second randomization performed.

A participant must be discontinued from study intervention but continue to be monitored in the study for any of the following reasons:

The participant or participant's legally acceptable representative requests to discontinue study intervention.

Hyperglycemia: The participant meets the criteria for rescue/intensification and rescue/intensification therapy is refused by the participant or deemed clinically inappropriate by the investigator.

- Hypoglycemia:
 - Repeated (2 or more episodes since the prior study visit)
 - FSG <54 mg/dL (3.0 mmol/L) with or without symptoms of hypoglycemia, OR
 - FSG 54 to 70 mg/dL (3.0 to 3.9 mmol/L) with symptoms of hypoglycemia, and without a reasonable explanation (such as increased physical activity and/or skipped meal).

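### Appendix 10 pathway B allows a Sponsor-approved restart without excluding ALT or AST ≥5X ULN for 2 weeks or longer, which Section 7.1 makes a permanent stop

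*Combined protocol and SAP*

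**What the plan says.** **Restart provisions (Appendix 10, Section I).** Pathway B covers ALT or AST ≥8X ULN, or ≥3X ULN with signs or symptoms of liver injury. Drug is interrupted, and enzymes are repeated "initially approximately 2-times per week, until resolution or return to baseline" (step 4). Under step 5, if a cause is established (the examples end with "cholecystitis, biliary obstruction), blinded investigational product may be restarted with approval by the Sponsor"), restart is possible; otherwise the participant discontinues. Pathway A covers ALT or AST ≥3X ULN with bilirubin ≥2X ULN. Its step 3 is stricter: restart is possible only if the cause of the raised "levels is established and the abnormalities resolve, blinded investigational product may be restarted with approval by the Sponsor".

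**Stopping provisions.** Section 7.1 introduces its list with "A participant must be discontinued from study intervention but continue to be monitored in the study for any of the following reasons". One liver criterion is ALT or AST ≥"5X ULN for 2 weeks or longer". Section 7.1 later states that discontinuation is permanent and that the participant may not resume study drug. The summary closing Section I of Appendix 10 begins "participants should be discontinued from blinded investigational product for any of the following reasons" and repeats the same 2-week criterion. The introduction to Section I, before a pathway is chosen, tells the investigator to "discontinue the participant from blinded investigational product if a prespecified criterion is met".

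**Link between the two.** Section 7.1 points to Appendix 10 for further detail on managing and discontinuing such participants. Neither place says which text prevails if they differ.

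**The concern.** A hepatic stopping rule should give one answer for one patient. A participant in pathway B with a proven cause and enzymes still at or above 5X ULN after 2 weeks gets two. Step 5 offers restart with Sponsor approval, while Section 7.1 requires an irreversible stop. Two sites could each follow text in the protocol and act in opposite ways, and a restart approved under step 5 would breach a mandatory rule in a pediatric trial.

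The situation is foreseeable. Section II of Appendix 10 plans further work-up for participants "whose elevated liver enzymes persist for more than 1-week", and step 4's testing of about twice a week gives roughly 2 × 2 = 4 results over 14 days, so the 2-week trigger would be seen.

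**Working it through.** No plan figure is at issue and no arithmetic decides the point. The check is whether one participant can satisfy a restart provision and a mandatory stop together.

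**1. Conditions side by side**

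| Provision | Known cause needed for restart, or exempting from stop? | Resolution required? | Addresses ≥5X ULN for ≥2 weeks? |
|---|---|---|---|
| Appendix 10, B step 5 (restart) | Yes | Not stated | No |
| Appendix 10, A step 3 (restart) | Yes | Yes | No |
| Section 7.1 and Appendix 10 summary, bilirubin criterion (stop) | Yes, exempts | – | – |
| Section 7.1 and Appendix 10 summary, ≥8X or symptomatic criterion (stop) | Yes, exempts | – | – |
| Section 7.1 and Appendix 10 summary, 2-week criterion (stop) | No exemption | – | Yes |
| Appendix 10, C step 4 (stop) | No exemption | – | Yes |

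The neighboring stop criteria are limited to cases without an established cause. The 2-week criterion is not. As written, a known cause does not exempt a participant from it.

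**2. Pathway B test case (illustrative values).** ALT is 10X ULN, hepatitis of proven cause is diagnosed, and ALT is still 6X ULN on day 15.
- B step 5: cause established, so restart is open to Sponsor approval.
- Section 7.1: ALT ≥5X ULN for more than 2 weeks, so discontinuation is mandatory and permanent.
- Appendix 10 summary: discontinue (*should*, where Section 7.1 says *must*).

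Both provisions apply.

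**3. Does an implied resolution condition help?** Step 4's testing until resolution could be read as a precondition for step 5, although step 5 does not say so. Suppose it is. A participant who was ≥5X ULN for 2 weeks and later recovered had already met the permanent-stop criterion. The conflict remains.

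**4. Pathway A test case.** ALT ≥5X ULN with bilirubin ≥2X ULN persists beyond 2 weeks, a cause is found, and everything later normalizes. A step 3 permits restart; Section 7.1 had already required a permanent stop. The overlap exists but is weaker. It arises only after resolution, and A step 2 sends the site to drug-induced liver injury guidance in the site binder, which is not among these documents and may settle it.

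**5. Where there is no conflict.** If ALT and AST fall below 5X ULN before 2 weeks, a participant with a known cause meets neither the 2-week criterion nor the two cause-limited criteria. Pathway C contains no Sponsor-approved restart step of this kind.

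**The case against.** **The 2-week rule belongs to pathway C.** This is the strongest reply. The Appendix 10 list is presented as a summary, its three bullets follow the order A, B, C, and the only operational 2-week step is C step 4. If Section 7.1 is read through its reference to Appendix 10, the conflict disappears. There is also a possible rationale: A and B interrupt drug at once, whereas C can continue it during monitoring. However, no text states the limit. Section 7.1 has no pathways, the summary makes any one reason sufficient, and the Section I introduction applies before a pathway is selected. The reading also stops an explained, asymptomatic 6X elevation at 2 weeks while leaving restart open for an explained 10X one of equal duration. The reply shows ambiguity and lowers confidence, but does not remove the literal conflict.

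**Permission versus duty, and sequence.** Step 5 permits and Section 7.1 commands, so withholding approval satisfies both. A participant still ≥5X ULN at 2 weeks is discontinued then, leaving no interrupted drug to restart. This is how a careful Sponsor would act, and it keeps the risk small. The permission nevertheless remains in the text without the exclusion.

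**Pathway A rests on unseen guidance.** This stands. Pathway A is included for consistency, not as an equal finding.

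**Conclusion.** The concern holds on the literal text, with moderate confidence. B step 5 leaves restart open in a case where Section 7.1 requires a permanent stop, and A step 3 does so in a weaker form. The conclusion assumes that the 2-week criterion in Section 7.1 means what it says, without an unstated restriction to pathway C.

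Severity is minor. The documents give no rate of such events, so no number of children is claimed; cases should be rare. Section 9.9 reports that every randomized participant has completed or left Phase A, so only remaining Phase B treatment is affected.

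Three stronger inferences are not supported:
- *That efficacy conclusions are at risk.* There is no effect on alpha, power or the Week 24 A1C tests. At most, the rule decides whether a rare participant is on drug for the Week 54 A1C and FPG summaries, which Section 9.6.1 limits to within-group changes.
- *That B step 5 also breaches Section 7.1 whenever a cause is known but enzymes have not resolved.* Below the 2-week threshold Section 7.1 does not require a stop, because its ≥8X or symptomatic criterion applies only without an established cause.
- *That the protocol directs restart in these cases.* It makes restart possible, subject to Sponsor approval.

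**What to change.** Add to B step 5, and for consistency to A step 3: *Restart is not allowed once ALT or AST has been ≥5X ULN for 2 weeks or longer (Section 7.1).* This removes only discretion that Section 7.1 already forbids and leaves the interrupt, evaluate and restart sequence otherwise intact.

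If the Sponsor intended a known cause to be an exception, the edit belongs elsewhere. The 2-week criterion in Section 7.1, C step 4 and the Appendix 10 summary would each need to be limited to cases without an established etiology. The Sponsor should choose one course; leaving the text as it stands keeps the ambiguity.

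A resolution requirement in B step 5 is not recommended as part of this correction. It resolves no conflict with Section 7.1, and the closing sentence of step 5 would then discontinue explained but unresolved cases that Section 7.1 does not stop.

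The cost is one sentence in each of two steps, with no new visits, data or analyses. Because a stopping rule changes, a protocol amendment with IRB/IEC approval is needed (Section 10.1.1). The documents mention no further amendment; if one is made, this edit could go with it. Until then, the Sponsor can comply with both texts by refusing restart in these cases.
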